### 5.1.2 Protocol Completion/Sample Destruction

All specimens obtained in the protocol are used as defined in the protocol. Any specimens that are remaining at the completion of the protocol will be stored in the conditions described in sections above. The study will remain open so long as sample or data analysis continues. Samples from consenting subjects will be stored until they are no longer of scientific value or if a subject withdraws consent for their continued use, at which time they will be destroyed. If the patient withdraws consent the participant's data will be excluded from future distributions, but data that have already been distributed for approved research use will not be able to be retrieved.

The PI will record any loss or unanticipated destruction of samples as a deviation. Reports will be made per the requirements of section 7.2.

## 6 DATA COLLECTION AND EVALUATION

### 6.1 DATA COLLECTION

The PI will be responsible for overseeing entry of data into an in-house password protected electronic system (Labmatrix) and ensuring data accuracy, consistency and timeliness. The principal investigator, associate investigators/research nurses and/or a contracted data manager will assist with the data management efforts. All data obtained during the conduct of the protocol will be kept in secure network drives or in approved alternative sites that comply with NIH security standards. Primary and final analyzed data will have identifiers so that research data can be attributed to an individual human subject participant.

All adverse events, including clinically significant abnormal findings on laboratory evaluations, regardless of severity, will be followed until return to baseline or stabilization of event.

Document AEs from the study procedure (see Section 3.2) through 14 days following study interventions.

An abnormal laboratory value will be recorded in the database as an AE **only** if the laboratory abnormality is characterized by any of the following:

- Results in discontinuation from the study
- Is associated with clinical signs or symptoms
- Requires treatment or any other therapeutic intervention
- Is associated with death or another serious adverse event, including hospitalization.
- Is judged by the Investigator to be of significant clinical impact
- If any abnormal laboratory result is considered clinically significant, the investigator will provide details about the action taken with respect to the test drug and about the patient's outcome.

Adverse Events related to endoscopy will **only** be recorded if they are serious (all Grades) or unexpected (Grades 3 and above).

**End of study procedures:** Data will be stored according to HHS, FDA regulations, and NIH Intramural Records Retention Schedule as applicable.

**Loss or destruction of data:** Should we become aware that a major breach in our plan to protect subject confidentiality and trial data has occurred, this will be reported expeditiously per requirements in Section [7.2.1](#).

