## **2 ELIGIBILITY ASSESSMENT AND ENROLLMENT**

### **2.1 ELIGIBILITY CRITERIA**

#### **2.1.1 Inclusion Criteria**

- Patients with CDH1 germline mutation known to be pathogenic or likely pathogenic, which may also be classified as “significant” or “likely significant” (patients with variants of “uncertain significance” are excluded).

**or**

- Patients with CTNNA1 and PALB2 germline mutations suspected to be, or reported to be, associated with HDGC.

**or**

- In the absence of a germline CDH1 mutation, patients must meet clinical criteria for genetic testing due to a history suggestive of Hereditary Diffuse Gastric Cancer (HDGC) syndrome ([Appendix A](#)).
- Age  $\geq$ 18 years.
- Physiologically able to undergo upper endoscopy.
- Ability to understand and the willingness to sign a written informed consent document.

- Pregnant women are eligible during second trimester of pregnancy if clinically indicated for evaluation of cancer.

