### 3.2.6 Post-discharge/Follow-up

- Patients will return to the NIH Clinical Center approximately two weeks after the EGD to discuss pathology results and any adverse events that they might have experienced. Alternatively, we will discuss pathology results and AEs on the phone.
- If patient elects to undergo gastrectomy, we will request stomach tissue to perform pathology assessment.

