## **3.3 CRITERIA FOR REMOVAL FROM PROTOCOL INTERVENTIONS AND OFF STUDY CRITERIA**

Prior to removal from study, effort must be made to have all subjects complete a safety visit approximately 14 days following study interventions.

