### 9.5.3 Risk/Benefit Analysis for Pregnant Women

The benefit is detection of gastric cancer at its earliest stage so that it is potentially curable. We will be following the anesthesia guidelines for pregnant women, i.e., waiting until the second trimester. All described risks described in Section 9.5.1 apply for pregnant women and there are also additional risks, including fetal loss, premature labor, and delivery.

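### Adverse event documentation ends at day 14 with no pregnancy-outcome follow-up, so obstetric events beginning later, of kinds section 9.5.3 names as risks, would not be systematically captured

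*Combined protocol and SAP*

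**What the plan says.** **Eligibility.** Section 2.1.1 states: "Pregnant women are eligible during second trimester of pregnancy if clinically indicated for evaluation of cancer". Section 9.4 supports their inclusion and withholds fluorescein from them.

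**Named risks.** After applying the general risks of section 9.5.1 to pregnant women, section 9.5.3 adds that "there are also additional risks, including fetal loss, premature labor, and delivery".

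**Collection window.** Section 6.1 instructs: "Document AEs from the study procedure (see Section 3.2) through 14 days following study interventions". It makes no separate provision for pregnant participants. For endoscopy-related events it also restricts recording to serious events of any grade and unexpected events of Grade 3 or above.

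**Scheduled contact.** Section 3.2.6 says: "Patients will return to the NIH Clinical Center approximately two weeks after the EGD to discuss pathology results and any adverse events", with a telephone discussion as the alternative. Section 3.3 asks, before removal from study, that "effort must be made to have all subjects complete a safety visit approximately 14 days following study interventions".

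**Beyond day 14.** Under section 6.1, adverse events "will be followed until return to baseline or stabilization of event". Section 7.3 asks for deaths within 30 days of a research intervention to be reported to the Clinical Director. Sections 7.2.1 and 7.2.2 refer to Policy 801, whose content is not reproduced. No section mentions delivery, pregnancy outcome or the newborn as data to be collected.

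**The concern.** The risk section and the data-collection section do not match in time. A woman who has the procedure in the second trimester is still well short of term when the window closes, so much of the period in which fetal loss or preterm labor could occur lies after the last scheduled contact. The rule that follows events to resolution needs an event to have been documented first, so it does not reach one that begins on day 15 or later.

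At stake is the safety record for a group whose inclusion the protocol justifies separately. CEM adds about 30 minutes of general anesthesia to the mapping endoscopy (section 3.1). A statement at the end of the study that no pregnancy complications were seen would cover two weeks per woman, and a reader could easily take it to cover the whole pregnancy.

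**Working it through.** The plan gives no calculated figure on this point. Its one relevant number is the 14-day window, stated directly in section 6.1. The sample-size figures in section 8.2 do not enter.

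**Step 1. Is there a route for a late event?** Take a fetal loss or preterm labor that begins on day 20.
- 6.1 documentation rule: closed at day 14.
- 3.2.6 and 3.3 contacts: both at about two weeks, so already past.
- 6.1 follow-to-resolution rule: no earlier event to follow.
- 7.3: concerns deaths within 30 days and does not mention fetal loss or preterm delivery.
- 7.2.1 and 7.2.2: depend on Policy 801, so the answer is unknown. The protocol schedules no contact at which the team would learn of the event.

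Systematic capture therefore stops at day 14. Ad hoc reporting after that cannot be excluded.

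**Step 2. How much time is unobserved?** Assumptions that are not in the documents: second trimester is weeks 14 to 27, and preterm means before week 37. With procedure week *w* and end week *e*, the share of remaining time covered is 2 / (*e* − *w*).

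| Procedure week | End week | Weeks remaining | Covered | Unobserved |
|---|---|---|---|---|
| 14 | 37 | 23 | 2/23 = 8.7% | 21/23 = 91% |
| 27 | 37 | 10 | 2/10 = 20% | 8/10 = 80% |
| 14 | 40 | 26 | 2/26 = 7.7% | 24/26 = 92% |
| 27 | 40 | 13 | 2/13 = 15.4% | 11/13 = 85% |

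The week-37 rows bear on preterm labor and delivery. The week-40 rows show the effect of following to term.

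**Step 3. Does a share of time give a share of events?** Only if risk is even over the remaining pregnancy. If procedure-related risk instead decays exponentially from the procedure with half-life *h* days, and the later cut-off at delivery is ignored, the share that begins inside the window is 1 − 0.5^(14/*h*).

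| Half-life (days) | Inside the window | Missed |
|---|---|---|
| 7 | 75% | 25% |
| 14 | 50% | 50% |
| 28 | 29% | 71% |
| 56 | 16% | 84% |

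The half-lives are illustrative, since the documents say nothing about when such events occur. Under this model a majority is missed only if the half-life exceeds 14 days.

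**The case against.** A reader might infer that most of the named events would be missed. The documents do not support that. Section 9.5.3 presents these as risks of taking part, alongside the procedural risks of 9.5.1. Events triggered by anesthesia or endoscopy may cluster soon after the procedure, when the window is open. Later events will also include ordinary background obstetric events, so unobserved time does not measure missed study harm. This objection stands, and it limits the conclusion to time and to systematic capture.

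A reader might also infer that a late event would be recorded nowhere, or that the investigators and the IRB could not act on it. That goes too far. Reporting under Policy 801 may reach a related event after day 14, but the policy's content is not available to settle it, and 7.3 shows that safety reporting as a whole does not stop at day 14. Preterm labor that begins on day 10 would be followed to resolution if documented.

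A third tempting reading is that participants leave the study at day 14. They do not. The off-study criteria in 3.3.2 contain no such limit, and the secondary endpoint depends on gastrectomy pathology that may come later. Only adverse event documentation ends.

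Finally, exposure is small. Pregnant women enter only where evaluation is clinically indicated, they receive no fluorescein, and the research increment is mainly CEM and its added anesthesia time. There is no comparator, and section 8 plans no analysis of pregnancy safety. This lowers the priority but does not close the gap between 9.5.3 and 6.1.

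**Conclusion.** The point holds in a limited form. The protocol names obstetric risks, ends adverse event documentation at day 14, schedules no later safety contact, and specifies no pregnancy-outcome follow-up. Obstetric events that begin after day 14 would not be systematically captured.

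On the assumed gestational weeks, 80% to 91% of the time to week 37 is unobserved. The share of procedure-related events missed cannot be estimated from the documents. In the illustrative scenarios above it runs from 25% to 84%. Reportability of later events under Policy 801 is undetermined.

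This is a low-priority improvement to safety data. The accrual ceiling is 40, few or perhaps no participants will be pregnant, and neither the primary nor the secondary endpoint is touched.

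**What to change.** Add to sections 6.1 and 3.2.6 a provision along these lines: *for participants who are pregnant at the time of the procedure, fetal loss, premature labor, preterm delivery and pregnancy outcome will be collected by telephone until the pregnancy ends, and reported under section 7.2.1 where they qualify.* The 14-day window for other participants stays as it is. Section 3.3.2 needs no change.

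The cost is a short amendment and one or two extra calls per pregnant participant. Section 3.2.6 already allows adverse events to be discussed by telephone, so no new procedure or staff is needed. The downside is a longer period of data collection for a few women. Without a comparator, any late events recorded would have to be described case by case and not attributed to the procedure by default.

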## **3 STUDY IMPLEMENTATION**

### **3.1 STUDY DESIGN**

This is a Phase II single arm study designed to evaluate the efficacy of CEM to detect signet ring cell foci within the gastric mucosa of patients with hereditary diffuse gastric cancer syndrome.

At the time of endoscopy, all patients will undergo white-light, upper endoscopy with systematic gastric mapping according to our current practice pattern and as outlined by IGCLC [12] (Section 3.2.2). In addition, during this endoscopy patients will undergo CEM using the Cellvizio probe (Mauna Kea Technologies) to scan the same anatomic zones as evaluated in the systematic gastric mapping approach (Section 3.2.3). Any abnormal areas visualized with the CEM probe will be biopsied. Patients are informed of the risks of endoscopy such as gastrointestinal bleeding and perforation. The standard gastric mapping requires approximately 30 minutes of general anesthesia time. The addition of CEM adds another 30 minutes of general anesthesia but no increase in risk of general complications such as bleeding or perforation.

All biopsies are sent to Laboratory of Pathology (see Section 5.1.1). In patients co-enrolled to protocol 13C0176, leftover biopsy samples will be used for research as described in 13C0176.

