#### **3.2.2 White-light, Upper Endoscopy**

At the time of endoscopy, all patients will undergo white-light, upper endoscopy with systematic gastric mapping according to IGCLC guidelines.[8] The anatomic zones are outlined below. From each of the five zones, 6 cold forceps biopsies and photos will be obtained. The total number of biopsies will be thirty. Any visibly abnormal areas will also be biopsied.

1. Antrum
2. Transitional Zone (antrum-body)
3. Body
4. Fundus

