### 9.5.1 Risks for All Participants Including Subjects Unable to Consent

#### *Risks of Upper Endoscopy*

The risks of upper endoscopy include, but are not limited to, temporary throat soreness, gastrointestinal bleeding, and rarely gastrointestinal perforation.

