#### *Risk of Biopsies*

All care will be taken to minimize risks that may be incurred by tumor sampling. Biopsies will be taken during endoscopy. All procedure-related risks (such as bleeding, infection and visceral injury) will be explained fully during informed consent.

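### Section 6.1 leaves expected, non-serious endoscopic bleeding unrecorded, and the planned data cannot support the Section 3.1 statement that confocal endoscopic microscopy adds no bleeding or perforation risk

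*Combined protocol and SAP*

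**What the plan says.** Three parts of the combined protocol and SAP bear on this point.

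- **Recording (Section 6.1).** Adverse events in general, "regardless of severity, will be followed until return to baseline or stabilization of event". Staff are also told to document events from the procedure to 14 days afterwards. A later sentence narrows this for endoscopy: related events will only "be recorded if they are serious (all Grades) or unexpected (Grades 3 and above".
- **Procedure and its risk (Sections 3.1 and 3.2.2).** Systematic mapping takes six biopsies from each of five zones: "The total number of biopsies will be thirty". Visibly abnormal areas are biopsied too. CEM follows in the same endoscopy, and "Any abnormal areas visualized with the CEM probe will be biopsied". Section 3.1 says that CEM "adds another 30 minutes of general anesthesia but no increase in risk of general complications such as bleeding or perforation".
- **Listed risks (Section 9.5.1).** For upper endoscopy these include "temporary throat soreness, gastrointestinal bleeding, and rarely gastrointestinal perforation". For biopsies the text reads: "All procedure-related risks (such as bleeding, infection and visceral injury) will be explained fully during informed consent". Fluorescein and general anesthesia have their own separate risk entries.

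Section 8 contains no safety endpoint or safety analysis.

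**The concern.** The trial adds a procedure to the screening of people whose stomachs usually look normal. What it adds physically is anesthesia time, from about 30 to about 60 minutes, and an unstated number of further biopsies. The harm those biopsies would most plausibly cause is minor bleeding, and the recording rule leaves out exactly that kind of event.

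Meanwhile Section 3.1 states without data that bleeding and perforation risk does not rise, in the same paragraph that calls for the extra biopsies. Anyone who later wants to describe the safety of the combined procedure would have no count of minor bleeds, and the reassuring sentence would stand untested.

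**Working it through.** **1. What the rule captures.** An endoscopy-related event enters the record if it is (a) serious, at any grade, or (b) unexpected and Grade 3 or above. Applied to bleeding:

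| Bleed | Recorded? |
|---|---|
| Serious, any grade | Yes, by (a) |
| Non-serious, Grade 1 or 2 | No, whether expected or not |
| Non-serious, Grade 3 or above, judged expected | No |
| Non-serious, Grade 3 or above, judged unexpected | Yes, by (b) |

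Section 7.1 refers to an outside policy for definitions. I assume that a risk listed in Section 9.5.1 counts as expected. That assumption matters only for the last two rows.

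**2. Does the plan hold a safety figure to reproduce?** No. It gives no bleeding rate, expected event count or safety power. The efficacy design in Section 8.2 (36 patients, 24% against 45%, one-sided 0.10 exact binomial) does reproduce. Rejecting at 13 or more of 36 gives an exact alpha of 0.070 and power of 0.893, against the stated 89%. Nothing here alters it.

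**3. What complete recording would give.** For zero events in n patients, the exact one-sided 95% upper bound is 1 − 0.05^(1/n).

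- n = 36 (evaluable target): 1 − 0.05^(1/36) = 8.0%
- n = 40 (accrual ceiling): 1 − 0.05^(1/40) = 7.2%

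Under the current rule these bounds would apply only to events that are serious or unexpected at Grade 3 or above.

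**4. How much could go unrecorded.** The documents give no rates, so the inputs below are assumptions. Let p be the true share of patients with a bleed and s the share of bleeds that are serious, with all bleeds treated as expected and at most one per patient. For n = 36, expected bleeds = 36p, recorded = 36ps, unrecorded = 36p(1 − s), and the chance of recording none = (1 − ps)^36.

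| p | s | Expected | Recorded | Unrecorded | P(none recorded) |
|---|---|---|---|---|---|
| 5% | 10% | 1.8 | 0.18 | 1.62 | 0.835 |
| 10% | 10% | 3.6 | 0.36 | 3.24 | 0.696 |
| 20% | 10% | 7.2 | 0.72 | 6.48 | 0.483 |
| 5% | 50% | 1.8 | 0.90 | 0.90 | 0.402 |
| 10% | 50% | 3.6 | 1.80 | 1.80 | 0.158 |
| 20% | 50% | 7.2 | 3.60 | 3.60 | 0.023 |

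If few bleeds are serious, a record with no bleeds is quite likely even when several patients bled.

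**5. Could full recording test the Section 3.1 statement?** Not by itself. The study has one arm, and mapping and CEM are done in one session. Complete counts would give the bleeding rate of the combined procedure. CEM's share could be approached only where a bleed can be traced to a mapping site or a CEM-directed site.

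**The case against.** The strongest reply is that limiting low-grade event capture is a matter of proportion. The devices are already marketed, Section 2.1.2 excludes patients on therapeutic anticoagulation or with bleeding disorders or thrombocytopenia, and no efficacy result depends on the choice. Events are also discussed at about two weeks (Section 3.2.6), a safety visit is sought at about 14 days (Section 3.3), and the principal investigator reviews each patient's events (Section 7.4.1). All of this is fair. It limits the weight of the point, but discussing or reviewing an event does not put it in the dataset when the rule says that it is not to be recorded.

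A reader might infer more than the documents support:

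- *That all expected bleeding goes uncounted.* Serious bleeding is recorded at every grade.
- *That Section 6.1 flatly contradicts itself.* One sentence is about following events and the later one about recording them. A general rule with a named exception is a possible reading, and the same section limits database entry of laboratory values in a similar way. The instruction to document events through 14 days makes this a tension to be resolved, not a plain contradiction.
- *That anesthesia and fluorescein reactions are also excluded.* Section 9.5.1 lists them apart from endoscopy risks, so they may fall under the general rule. The plan does not say.
- *That CEM raises the biopsy count by 73%.* The scan list in Section 3.2.3 has 4 + 4 + 4 + 4 + 3 + 3 = 22 views, and 22/30 = 73%. But a view is biopsied only if it looks abnormal, and no number is forecast. Section 1.2 also describes earlier mapping at the site with 88 biopsies in 22 locations; if that is per procedure, 30 + 22 = 52 is well below it.
- *That Section 9.5.1 disproves Section 3.1.* One lists the risks of endoscopy and biopsy in general and the other speaks of CEM's increment. The 3.1 sentence is unsupported; it is not shown to be false.

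**Conclusion.** The point holds as a modest gap in safety data. Expected, non-serious bleeding related to endoscopy is not recorded, and the statement of no added bleeding or perforation risk rests on nothing that the trial will measure.

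It is tempting to blame the recording rule alone for that second failing. The documents do not support this: the main cause is the absence of any patient without CEM, and the rule is a second cause. Nor do they support saying that the trial sets out to demonstrate safety, since Section 8 plans no such conclusion.

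The size cannot be fixed from the documents. Under the assumed rates above, between 0.9 and 6.5 bleeds in 36 patients would go unrecorded. The conclusion rests on reading the rule literally and on bleeds from CEM-directed biopsies counting as related to endoscopy. For non-serious bleeds of Grade 3 or above, it also rests on listed risks being treated as expected.

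**What to change.** 1. In Section 6.1, reconcile the restriction on endoscopy events with the sentences on following all adverse events and documenting them through 14 days. State whether events from CEM, anesthesia and fluorescein count as related to endoscopy.
2. Record bleeding and perforation at every grade through day 14. Add the number of CEM-directed biopsies per patient and, where identifiable, whether the source was a mapping site or a CEM-directed site.
3. In Section 8, add a descriptive report of these counts with exact confidence intervals.
4. In Section 3.1, word the statement on bleeding and perforation as an expectation that this trial does not test.

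The cost is a few extra form entries for at most 40 patients, at a contact already planned for about two weeks, plus short text edits. Even then, the data would describe the combined procedure and would not isolate CEM's increment.
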